8.3.6 SERIOUS ADVERSE EVENT REPORTING

Once [name] (or a co-investigator) is contacted about a serious adverse event, she / he will make a determination about the reporting requirements in accordance with UNC IRB guidelines. This will include notification of the UNC IRB within 24-hours if a study-related death and within 48 hours if another SAE.

All SAEs will be reported to the NIAMS (through the NIAMS Executive Secretary) within 48 hours of the investigator becoming aware of the event. The SAE Report Form will be completed and the SO's review of the SAE report will be shared with the NIAMS once received.

8.3.7 REPORTING EVENTS TO PARTICIPANTS

N/A

8.3.8 EVENTS OF SPECIAL INTEREST

N/A

8.3.9 REPORTING OF PREGNANCY

N/A

8.4. UNANTICIPATED PROBLEMS

8.4.1 DEFINITION OF UNANTICIPATED PROBLEMS

This protocol uses the definition of Unanticipated Problems as defined by the Office for Human Research Protections (OHRP). OHRP considers unanticipated problems involving risks to participants or others to include, in general, any incident, experience, or outcome that meets all of the following criteria:

- (1) Unexpected (in terms of nature, severity, or frequency) given (a) the research procedures that are described in the IRB-approved research protocol and informed consent document; and (b) the characteristics of the participant population being studied;
- (2) Related or possibly related to participation in the research. *Possibly related* means there is a reasonable possibility that the incident, experience, or outcome may have been caused by the procedures involved in the research); and
- (3) Suggests that the research places participants or others at a greater risk of harm (including physical, psychological, economic, or social harm) than was previously known or recognized.

OHRP recognizes that it may be difficult to determine whether a particular incident, experience, or outcome is unexpected and whether it is related or possibly related to participation in the research. OHRP notes that an incident, experience, or outcome that meets the three criteria above generally will warrant consideration of substantive changes in the research protocol or informed consent process/document or other corrective actions in order to protect the safety, welfare, or rights of participants or others.

The following corrective actions or substantive changes that could be considered in response to an unanticipated problem include:

- Changes to the research protocol initiated by the investigator prior to obtaining IRB approval to eliminate apparent immediate hazards to subjects;
- modification of inclusion or exclusion criteria to mitigate the newly identified risks;
- implementation of additional procedures for monitoring subjects; suspension of enrollment of new subjects;
- suspension of research procedures in currently enrolled subjects;

- modification of informed consent documents to include a description of newly recognized risks;
- provision of additional information about newly recognized risks to previously enrolled subjects.

Only a small subset of adverse events occurring in human subjects participating in research will meet these three criteria for an unanticipated problem. Furthermore, there are other types of incidents, experiences, and outcomes that occur during the conduct of human subjects research that represent unanticipated problems but are not considered adverse events. For example, some unanticipated problems involve social or economic harm instead of the physical or psychological harm associated with adverse events. In other cases, unanticipated problems place subjects or others at increased risk of harm, but no harm occurs.

8.4.2 UNANTICIPATED PROBLEMS REPORTING

All UPs will be reported to UNC IRB within 48 hours of the PI becoming aware of the event. All UPs will be reported to the NIAMS and the SO (through the NIAMS Executive Secretary) within 48 hours of the PI becoming aware of the event.

8.4.3 REPORTING UNANTICIPATED PROBLEMS TO PARTICIPANTS

Participants will be given any new information gained during the course of the study that might affect their willingness to continue participation in the study.

9 STATISTICAL CONSIDERATIONS

9.1 STATISTICAL HYPOTHESES

The aim of this study is to conduct an exploratory randomized controlled trial with 60 patients with knee and / or hip OA equally randomized to OA CARE or a usual care (UC) control group. Sub-aims and associated hypotheses are:

Aim 1. Assess the feasibility and acceptability of OA CARE. There are no specific hypotheses associated with this aim. Analyses will be descriptive in nature.

Aim 2. Obtain preliminary data on the efficacy of OA CARE with respect to the primary outcome of change in total Western Ontario and McMaster Universities Osteoarthritis Index (WOMAC) score. We hypothesize that participants in OA CARE will have clinically meaningful improvements in WOMAC scores at 6- and 12-month follow-up relative to a UC control group. Similarly, we hypothesize that participants in OA CARE will have greater improvements in secondary and exploratory outcomes compared with the control group.

9.2 SAMPLE SIZE DETERMINATION

Due to the exploratory nature of this trial, the objective is to inform estimates for a larger RCT. Accordingly, we do not necessarily expect this trial to be highly powered. However, we do note that for the projected total of n=60 enrolled participants, equally allocated between the two arms of the trial at the two-sided 0.05 significance level, and accounting for a conservative effect of clustering within the OA CARE arm, we would exceed 80% power to detect an effect size of at least 1.7 SD. This choice of sample size is deemed to be feasible for completion within the time frame of this exploratory trial and will allow sufficient experience with intervention delivery to inform the larger trial. We expect some drop-out and loss-to-follow-up among participants, and this exploratory trial will contribute to our sample size estimation for the larger RCT in this regard. However, based on rates of drop-out in prior trials ^{28,29,31}, our target sample size of 60 participants will allow ample experience with study procedures. Our analytic strategy (described below) will also accommodate missing data due to dropout, missed visits, and loss-to-follow-up.

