9.4 STATISTICAL ANALYSES PLAN

The primary patient outcome of the total WOMAC score will be statistically analyzed between experimental groups across the follow-up time points through a general linear mixed model (GLMM). Fixed effects will include indicators for the *OA CARE* group, the 12-month follow-up time point, and their interaction (group by time). Additional fixed effects will be baseline total WOMAC score and possibly any covariates exhibiting random imbalance between groups. Random effects will be included for patients (to account for their repeated measures) and for grouping within the *OA CARE* arm (e.g. 10-participant Weight Management Program groups) to account for clustering. Customized statistical linear contrasts will be constructed to estimate the effect size via the difference in means for *OA CARE* versus usual care, along with the corresponding 95% confidence limits, separately at 6- and 12- months, to provide useful estimates that will inform the sample size estimation for the subsequent trial. Estimated correlations among the follow-up time points, as well as estimated within-cluster intraclass correlation for the *OA CARE* arm, will also be useful in this regard.

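### Does the 1.7 SD detectable effect, stated without the clustering and degrees-of-freedom inputs behind it, call for a change to the plan?

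*Combined protocol and SAP*

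**What the plan says.** Section 9.2 opens by explaining that "the objective is to inform estimates for a larger RCT" and that high power is not necessarily expected. It then notes, for 60 participants split equally at a two-sided 0.05 level and "accounting for a conservative effect of clustering within the OA CARE arm", that "we would exceed 80% power to detect an effect size of at least 1.7 SD". It justifies the number enrolled by what is feasible in the time available. On attrition it says "We expect some drop-out and loss-to-follow-up among participants" and gives no rate.

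Section 9.4 specifies a mixed model with random effects for patients and for OA CARE groups, giving as its example "10-participant Weight Management Program groups". On covariates: "Additional fixed effects will be baseline total WOMAC score". The group difference is to be reported "along with the corresponding 95% confidence limits, separately at 6- and 12- months". Among the outputs meant to help size the next trial it lists "Estimated correlations among the follow-up time points, as well as estimated within-cluster intraclass correlation for the" OA CARE arm. It states no df method and no interval for the ICC.

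Section 4.2 says the trial is not powered to test efficacy.

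**The concern.** An effect of 1.7 SD is very large. Without clustering, 30 per arm has 80% power at about 0.72 SD, so the gap between 0.72 and 1.7 comes entirely from inputs that Section 9.2 does not state. Very different inputs lead to the same 1.7. Because Section 9.4 adjusts for baseline WOMAC, the SD could also be the raw or the adjusted one. A reader cannot tell what the trial can detect or how wide its intervals will be, although estimation is its stated purpose.

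The second worry is the analysis. The OA CARE mean rests on about three groups. If the 95% limits used normal quantiles they would be too narrow once groups differ appreciably. An ICC from three groups is very imprecise, and reported alone it could mislead whoever sizes the next trial.

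**Working it through.** **Inputs from the documents.** 60 participants, 30 per arm, two-sided 0.05, 80% power (Section 9.2). Groups of about 10 (Sections 6.1 and 9.4), so 30/10 = 3 OA CARE groups. Randomization blocks of 20 with equal allocation (Section 4.1) put 10 OA CARE participants in each block, and 60/20 = 3 blocks, which agrees.

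**Assumptions.** ICC shown as a range, total SD = 1 in each arm, no dropout unless stated. The documents give no ICC.

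**Formulas.** Only the OA CARE arm is clustered:

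- v1 = [1 + 9 × ICC]/30, v2 = 1/30, SE = √(v1 + v2)
- Detectable effect, normal quantiles = (1.96 + 0.84) × SE = 2.80 × SE
- Satterthwaite df = (v1 + v2)² / (v1²/2 + v2²/29), with power from the t distribution on those df

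**The plan's own figure.** With no clustering, SE = √(2/30) = 0.258 and the detectable effect is 0.72 SD. Three of the bases that give 1.7 SD are:

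- ICC = 1, normal quantiles: SE = √(10/30 + 1/30) = 0.606, effect 1.696 SD, power at 1.7 SD = 0.802
- ICC about 0.33, Satterthwaite df
- ICC about 0.08, 2 df

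The first is the extreme case in which each group acts as one observation. It fits an allowance described as conservative and a claim to exceed 80%, but that reading is an inference.

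**Is the claim false anywhere plausible?**

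| Assumed ICC | Satterthwaite df | Detectable effect: normal / Satterthwaite / 2 df | Power at 1.7 SD: normal / Satterthwaite / 2 df |
|---|---|---|---|
| 0.01 | 6.9 | 0.74 / 0.86 / 1.49 | >0.99 / >0.99 / 0.87 |
| 0.05 | 5.5 | 0.80 / 0.98 / 1.62 | >0.99 / 0.997 / 0.83 |
| 0.10 | 4.6 | 0.87 / 1.12 / 1.76 | >0.99 / 0.986 / 0.78 |

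Power at 1.7 SD falls below 80% only if the ICC exceeds about 0.33 (Satterthwaite) or about 0.08 (the harsher 2 df). With normal quantiles it holds at every ICC. The Satterthwaite effects are approximate, since they treat the variances behind the df as known; simulating the estimated-variance procedure gave about 0.91, 1.03 and 1.19 SD. With an assumed 20% dropout (groups of 8, 24 in usual care) the Satterthwaite effects are 0.96, 1.06 and 1.19 SD, still well under 1.7.

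**Expected 95% half-width, no dropout.** Normal: 0.52, 0.56 and 0.61 SD at ICC 0.01, 0.05 and 0.10. Satterthwaite: 0.63, 0.71 and 0.82 SD.

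**Coverage if normal limits were used.** Simulation of three groups of 10 against 30 individuals, one time point, group variance truncated at zero: 95.1, 94.0, 92.6 and 90.3% at ICC 0.01, 0.05, 0.10 and 0.20. Satterthwaite limits gave 96.4, 95.7, 94.9 and 93.8%. The second set depends on how df are set when the group variance is estimated as zero: applying the plain formula throughout gave 98.2, 97.6, 96.8 and 95.5%.

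**The ICC estimate.** With three groups of 10 it is zero or below in 59, 47 and 37% of trials at true ICC 0.01, 0.05 and 0.10. An estimate of 0.05 has an exact 95% interval of −0.07 to 0.86.

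**The case for a change.** The best case for a change is that a pilot meant to inform estimates should be justified by precision, and that the open choices affect the reported limits. At an assumed ICC of 0.05 the half-width is 0.56 SD with normal quantiles and 0.71 SD with Satterthwaite df, and the exploratory tests in Section 9.4 use the same contrasts at 0.05. An ICC quoted without an interval could be taken at face value. For an assumed target of 0.4 SD with groups of 10 in one arm, the next trial would need 99, 121 or 196 per arm if sized on an ICC of 0, 0.05 or 0.22, and 0.22 is the 90th percentile of the estimate when the truth is 0.05. The remedy would cost only wording.

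The omissions stand, and so does the imprecision of the ICC. The harm does not follow from the plan as written. Silence on df is not a choice of normal quantiles, and a statistician fitting a group random effect with three levels would ordinarily use a small-sample method. An interval for the ICC can be computed from the same fit at reporting. The 99-to-196 range supposes that the next trial would be sized on one ICC point estimate, whereas Section 9.4 says only that the estimate will be useful, alongside the effect estimates with their limits. How a later trial is sized is for that trial's protocol.

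**Conclusion.** The concern does not call for a change. The gap is one of reporting: the ICC, df and SD behind 1.7 SD are unstated, so the figure cannot be checked to a single basis. It is an aside in a section that rests the sample size on feasibility, and it errs towards pessimism for most plausible inputs. Writing the inputs down would leave 60 participants, the model and the contrasts as they are.

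The df method matters more, but the loss arises only if the analysts choose normal limits: about one percentage point of coverage at ICC 0.05, and 2 to 5 points at 0.10 to 0.20. Satterthwaite or Kenward-Roger df (the latter not evaluated here) are routine options within the planned model, and an ICC interval needs no further data.

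These conclusions rest on three groups of 10, which follows from Sections 4.1, 6.1 and 9.4, and on assumed ICCs that the documents neither support nor exclude. An ICC well above 0.10 would make normal limits clearly too narrow, and the same small-sample choice would largely deal with that.

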9.3 POPULATIONS FOR ANALYSES

The primary analyses will be conducted using an intent-to-treat approach. Supportive exploratory analyses may be conducted to consider samples with greater completion of study intervention visits. Since this is an exploratory trial, the nature of these supportive analyses will be based on observed patterns of intervention contacts.

9.4 STATISTICAL ANALYSES PLAN

The primary patient outcome of the total WOMAC score will be statistically analyzed between experimental groups across the follow-up time points through a general linear mixed model (GLMM). Fixed effects will include indicators for the *OA CARE* group, the 12-month follow-up time point, and their interaction (group by time). Additional fixed effects will be baseline total WOMAC score and possibly any covariates exhibiting random imbalance between groups. Random effects will be included for patients (to account for their repeated measures) and for grouping within the *OA CARE* arm (e.g. 10-participant Weight Management Program groups) to account for clustering. Customized statistical linear contrasts will be constructed to estimate the effect size via the difference in means for *OA CARE* versus usual care, along with the corresponding 95% confidence limits, separately at 6- and 12- months, to provide useful estimates that will inform the sample size estimation for the subsequent trial. Estimated correlations among the follow-up time points, as well as estimated within-cluster intraclass correlation for the *OA CARE* arm, will also be useful in this regard.

Exploratory testing of efficacy will also be conducted using these statistical contrasts. The approach outlined above will be repeated separately for the WOMAC pain and function subscale scores, as well as for the secondary outcomes identified above. If any of these outcomes exhibit distributions that deviate markedly from normality, alternatives will include transformations to normalize the distribution and variable categorization with appropriate data analysis (e.g., mixed-effects logistic models or logistic models utilizing generalized estimating equations to accommodate correlated observations). An intent-to-treat approach will be followed in these analyses to provide a conservative approach. A two-sided 0.05 significance level will be applied to each outcome with no adjustment for multiple comparison in keeping with the exploratory nature of the trial. The GLMM approach utilizes all available follow-up data and accommodates missing data under a missing at random (MAR) paradigm. If missing data are extensive and deemed not to be MAR, analyses will be conducted using multiple imputation, yielding complete data for all participants. The feasibility and acceptability metrics will be summarized through descriptive statistics, along with corresponding 95% confidence intervals, separately by experimental arm when appropriate. This includes frequencies and proportions of patients who are eligible, who consent to participate in the study, who complete follow-up assessments, who meet criteria for and are interested in each type of additional intervention (at 6-month follow-up), and who use of these services during the study period. Means and standard deviations will be computed for the number of intervention visits attended by participants.

10 SUPPORTING DOCUMENTATION AND OPERATIONAL CONSIDERATIONS

10.1 REGULATORY, ETHICAL, AND STUDY OVERSIGHT CONSIDERATIONS

10.1.1 INFORMED CONSENT PROCESS

10.1.1.1 CONSENT AND OTHER INFORMATIONAL DOCUMENTS PROVIDED TO PARTICIPANTS

Consent forms describing in detail the study intervention, study procedures, and risks will be given to the participant and written documentation of informed consent will be completed prior to starting the study intervention. The following consent materials are submitted with this protocol: Adult Consent Form.

10.1.1.2 CONSENT PROCEDURES AND DOCUMENTATION

Once a potential participant meets the medical record and telephone screening criteria for eligibility, and is interested in participating, they will be asked to attend a baseline visit that will involve completion of consent, baseline assessments and receipt of an accelerometer. No other study activities will occur until this process is completed.

We will use a UNC IRB approved consent form / script with included language that satisfies the HIPAA requirements and outlines the protection of health information utilized in the study.

Written informed consent will be obtained by a trained study team member. The study team member will read the IRB approved consent form to the potential participant and provide an opportunity for him/her to ask any questions that they may have about the research study. We anticipate this process to take approximately 20 minutes, but this time will not be limited should a participant have additional questions or concerns regarding the study. During this phase of the consent process, it will be stressed that the participant is not obligated to participate in the study, that participation is completely voluntary, and that he/she may withdrawal from the study at any time without penalty. Also, potential risks from participating in the study will be outlined in the consent form, as are the measures taken to protect against study specific risks. Once the information in the consent form is fully reviewed and understood by the individual, he/she will be asked to decide at that time if they would like to voluntarily participate in the research study. If the individual does choose to participate in the study, both the study team member and the participant will sign two copies of the informed consent form. The participant will receive one copy for their records and the other copy will be stored in a locked file cabinet of a study team member.

If after review of the consent form, the potential participant is not sure they would like to participate in the study at this time, they may choose to consider the study further, and then contact the study team if they decide later that they would like to participate.

Once informed consent has been collected, the study team member will collect written HIPAA authorization, and no activities will commence until this is received by the study team.

Participants will only be included if they have capacity to give legally effective consent. Additionally, this study will only recruit participants whom are English speakers.

10.1.2 STUDY DISCONTINUATION AND CLOSURE

This study may be temporarily suspended or prematurely terminated if there is sufficient reasonable cause. Written notification, documenting the reason for study suspension or termination, will be provided by the suspending or terminating party to study participants, investigator, funding agency, and regulatory authorities. If the study is prematurely terminated or suspended, the PI will promptly inform study participants, the IRB, and sponsor/funding agency and will provide the reason(s) for the termination or suspension. Study participants will be contacted, as applicable, and be informed of changes to study visit schedule.

Circumstances that may warrant termination or suspension include, but are not limited to:

- Determination of unexpected, significant, or unacceptable risk to participants
- Demonstration of efficacy that would warrant stopping
- Insufficient compliance to protocol requirements
- Data that are not sufficiently complete and/or evaluable
- Determination that the primary endpoint has been met

- Determination of futility

The study may resume once concerns about safety, protocol compliance, and data quality are addressed, and satisfy the funding agency, sponsor, IRB or other relevant regulatory or oversight bodies (OHRP, SO).

10.1.3 CONFIDENTIALITY AND PRIVACY

Participant confidentiality and privacy is strictly held in trust by the participating investigators, their staff, the safety and oversight monitor(s), and the sponsor(s) and funding agency. This confidentiality is extended to the data being collected as part of this study. Data that could be used to identify a specific study participant will be held in strict confidence within the research team. No personally-identifiable information from the study will be released to any unauthorized third party without prior written approval of the sponsor/funding agency.

Personal health information (e.g. patient name and contact information) will be shared with YMCA so they may contact participants to enroll in the medical membership and participate in programs. Any information shared between approved UNC study team members and YMCA personnel will be done verbally by phone, by encrypted email or a UNC IRB approved platform for sharing PHI.

All research activities will be conducted in as private a setting as possible.

The study monitor, other authorized representatives of the sponsor or funding agency, representatives of the IRB, regulatory agencies or representatives from companies or organizations supplying the product, may inspect all documents and records required to be maintained by the investigator, including but not limited to, medical records (office, clinic, or hospital) and pharmacy records for the participants in this study.

The study participant's contact information will be securely stored on a secure study database for internal use during the study. At the end of the study, all records will continue to be kept in a secure location for as long a period as dictated by the reviewing IRB, Institutional policies, or sponsor/funding agency requirements.

Study participant research data, which is for purposes of statistical analysis and scientific reporting, will be stored on a secure UNC server. The study data entry and study management systems used by research staff will be secured and password protected. At the end of the study, all study databases will be de-identified and archived on a secure UNC server.

Measures Taken to Ensure Confidentiality of Data Shared per the NIH Data Sharing Policies

It is NIH policy that the results and accomplishments of the activities that it funds should be made available to the public (see <https://grants.nih.gov/policy/sharing.htm>). The PI will ensure all mechanisms used to share data will include proper plans and safeguards for the protection of privacy, confidentiality, and security for data dissemination and reuse (e.g., all data will be thoroughly de-identified and will not be traceable to a specific study participant). Plans for archiving and long-term preservation of the data will be implemented, as appropriate.

Certificate of Confidentiality

To further protect the privacy of study participants, the Secretary, Health and Human Services (HHS), has issued a Certificate of Confidentiality (CoC) to all researchers engaged in biomedical, behavioral, clinical or other human subjects research funded wholly or in part by the federal government. Recipients of NIH funding for human subjects research are required to protect identifiable research information from forced disclosure per the terms of the NIH Policy (see <https://humansubjects.nih.gov/coc/index>). As set forth in [45 CFR Part 75.303\(a\)](#) and [NIHGPS Chapter 8.3](#), recipients conducting NIH-supported research covered by this Policy are

required to establish and maintain effective internal controls (e.g., policies and procedures) that provide reasonable assurance that the award is managed in compliance with Federal statutes, regulations, and the terms and conditions of award. It is the NIH policy that investigators and others who have access to research records will not disclose identifying information except when the participant consents or in certain instances when federal, state, or local law or regulation requires disclosure. NIH expects investigators to inform research participants of the protections and the limits to protections provided by a Certificate issued by this Policy.

